**Table 7: Venetoclax Dose Levels**

| Cohort                                | Dose Level | Target Dose of Venetoclax* |
|---------------------------------------|------------|----------------------------|
| Arm 1, Cohort 1
(FL)               | Level 1    | 800 mg by mouth daily      |
|                                       | Level (-1) | 600 mg by mouth daily      |
| Arm 2, Cohort 2
(MZL, MCL and CLL) | Level 1    | 400 mg by mouth daily      |
|                                       | Level (-1) | 200 mg by mouth daily      |

\*Stated dose of venetoclax is the target (maximum) dose.

**Table 8: Venetoclax dose-finding rules for Arms 1 and 2**

| Number of Patients with DLT at a Given Dose Level | Dose-Finding/Dose Decision Rules   |
|---|--|
| <2 out of 6                                       | This target dose will be used in expansion phase   |
| $\geq 2$ out of 6 at DL1                          | Six (6) patients will be entered at dose level (-1).   |
| $\geq 2$ out of 6 at DL (-1)                      | Further enrollment will be stopped, and a safety analysis will be performed to determine further course of action. |

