#### 3.1.1 Dose-Finding Phase

The dose-finding phase will assess the safety of venetoclax when added to obinutuzumab and magrolimab. Up to 6 FL patients in Arm 1 will be treated and undergo DLT assessment during the first 4 weeks (Cycle 1) of triplet combination therapy with magrolimab, obinutuzumab and venetoclax. Venetoclax will be administered at DL1 without a safety ramp-up ([Figure 3](#)). If  $\geq$

patients experience DLT at DL1, up to 6 additional patients will be enrolled (Cohort 1, Arm 1) and treated at DL(-1) of venetoclax. Dose-finding will follow the rules mentioned in **Table 8**.

Up to 6 MZL, MCL or CLL patients treated in Arm 2 will undergo DLT assessment during the first 5 weeks of triplet combination therapy (Cycle 1). Venetoclax will be administered with a safety ramp-up to target dose (dose level 1) (**Table 10, Figure 4**). If  $\geq 2$  patients experience a DLT at DL1, up to 6 additional patients will be enrolled (Cohort 2, Arm 2) and treated at DL (-1) of venetoclax (**Figure 3**). Dose-finding will follow the rules mentioned in **Table 8**.

No more than 2 patients can be in a DLT assessment period at any given time. If a DLT has occurred, only 1 patient can be in the respective DLT assessment period at a given time. Patients who withdraw before completing DLT assessment for reasons other than a DLT, will not be evaluable for assessment of DLT for dose review decisions, and will be replaced.

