**Figure 3: Arm 1: FL Dose-finding**

**Figure 4: Arm 2: MZL, MCL and CLL Dose-finding**

**Figure 5: Arms 3 and 4 – Dose Expansion**

### 3.1.4 Dose-Limiting Toxicity

Dose limiting toxicities (DLTs) will be assessed during the venetoclax dose-finding for Arms 1 and 2 as follows:

- the first 4 weeks of triplet combination therapy for patients enrolled in Arm 1, Cohort 1 (C1D1 to C1D28)

- the first 5 weeks after starting venetoclax in Arm 2, Cohort 2 (C1D1 to C1D35).

Dose reductions of magrolimab and obinutuzumab are not permitted during DLT assessment period.

A DLT for this study is defined as any grade 3 or higher adverse event that is clinically relevant and deemed probably or definitely related to any of the study drugs or to the combination therapy, in the opinion of the Principal Investigator and occurs during the venetoclax dose-finding period with the exception of following:

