#### 3.1.4.2 Hematologic AEs

- Grade 3 neutropenia not associated with clinical sequelae
- Grade 3 thrombocytopenia not associated with  $\geq$  grade 2 bleeding
- Grade 3 anemia that lasts less than 3 days and responds to blood transfusion. **NOTE:** Grade 3 hemolytic anemia that requires hospitalization or prolongation of existing hospitalization, is disabling, or limits self-care activities of daily life (ADLs) will be considered a DLT.
- Grade 3 or 4 lymphopenia

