Based on these estimates, up to 24 patients may be required for venetoclax dose-finding. These, in addition to 42 total treated patients required to complete the dose expansion phase brings the total number of patients required to complete the study to 66. To allow for a small number of inevaluable patients and screen failures, the accrual ceiling will be set at 76 patients. It is expected that 3 to 4 years may be required to complete accrual, including dose-finding and expansion cohorts. Patients enrolled in dose-finding cohorts who are treated at the same dose-level as the expansion cohorts may be analyzed together with the dose-expansion cohorts at the end of the study (Cohort 1 with Cohort 3, and Cohort 2 with Cohorts 4, 5 and 6, respectively).

As mentioned earlier in Section [1.2.6.2.1.2](#), recent reports indicate that MZL patients may be at a higher risk of infection-related AEs with fatal outcome when obinutuzumab was used in combination with chemotherapy. As an early stopping rule, if  $\geq 2$  subjects have infection-related SAEs or any subject experiences a fatal infection-related AEs from the first 6 subjects on study, we will hold further enrollment, and a comprehensive safety analysis will be performed.

In addition, an early stopping rule will be implemented for all histologies, if a substantial number of patients have to discontinue therapy due to unacceptable toxicity. If at any point after the first 20 patients are enrolled, 25% or more patients have been unable to complete therapy due to unacceptable toxicity or if at any point 2 or more deaths or grade 4 hemolytic anemia events occur that are probably or definitely related to study therapy, then study enrollment for all histologies will be suspended for a formal assessment of the overall safety profile of the study design. This early stopping rule is applicable throughout the duration of the study.

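### Table 8 counts a single related death among six dose-finding patients as one ordinary DLT, so with no other DLT the dose goes to expansion and, outside the infection rule, nothing requires a hold or safety analysis first

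*Combined protocol and SAP*

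**What the plan says.** **What counts as a DLT.** Section 3.1.4: "A DLT for this study is defined as any grade 3 or higher adverse event that is clinically relevant" and that the Principal Investigator judges probably or definitely related. The exceptions in 3.1.4.1 and 3.1.4.2 are all grade 3 events, apart from "Grade 3 or 4 lymphopenia". None concerns grade 5, so a related death is one DLT.

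**What follows from the count.** For fewer than 2 of 6 patients with DLT, Table 8 says "This target dose will be used in expansion phase". At 2 or more of 6 at DL1, six patients enter at DL(-1). At 2 or more of 6 at DL(-1), it says "Further enrollment will be stopped, and a safety analysis will be performed to determine further course of action". No row refers to grade.

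**Accrual after a DLT (3.1.1).** "If a DLT has occurred, only 1 patient can be in the respective DLT assessment period at a given time".

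**Stopping rules in Section 10.2.**
- All histologies: enrollment is suspended "if at any point 2 or more deaths or grade 4 hemolytic anemia events occur that are probably or definitely related to study therapy".
- All histologies, but only after the first 20 patients are enrolled: enrollment is suspended if "25% or more patients have been unable to complete therapy due to unacceptable toxicity".
- Infection: one fatal infection-related event, or two or more subjects with infection-related SAEs, among the first six subjects holds enrollment for a comprehensive safety analysis. The rule is introduced as a response to MZL data, and Section 1.2.6.2.1.2 describes early stopping rules for the MZL cohort. The rule itself names no histology.

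**The concern.** Section 1.2.8.1 says that no study had combined magrolimab with obinutuzumab, so the six-patient cohorts are the main safety gate for this triplet. The protocol itself reports fatal events with the component drugs:
- febrile neutropenia, pneumonia and sepsis with magrolimab (12.3.1);
- TLS with obinutuzumab (4.1.2.4);
- a sudden death in a patient with TLS on venetoclax (1.2.5.1);
- five fatal events among 212 patients on venetoclax with obinutuzumab (1.2.7.1).

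Most of these could occur outside MZL, and not all are infections.

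A gate that ignores grade treats a related death like a qualifying grade 3 event, and Table 8 words the step to expansion as automatic. Up to 18 FL patients, or 24 MZL, MCL and CLL patients (6 + 12 + 6), could then enter an expansion built on that dose. The plan is also uneven: one fatal infection is enough to hold enrollment under a rule written with MZL in mind, while one fatal TLS is not.

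**Working it through.** **The plan's own figures.** Dose-finding is 4 × 6 = 24 patients and expansion is 18 + 6 + 12 + 6 = 42. The total is 66, as Section 10.2 states. The documents give no operating characteristics for Table 8, so there is no stated error rate to reproduce.

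**Step 1: apply each rule to one related death in the DLT window, with no other DLT.**

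| Rule | Threshold | Count | Acts? |
|---|---|---|---|
| Table 8 | 2 of 6 with DLT | 1 of 6 | No; dose goes to expansion |
| 10.2, deaths or grade 4 hemolytic anemia | 2, pooled | 1 | No |
| 10.2, unable to complete therapy | 25% once 20 are enrolled (5 of 20) | 1, and the rule is not yet active | No |
| 10.2, infection | 1 fatal infection in the first six subjects | depends on cause and on which histologies are covered | Only for infection |
| 3.1.1, accrual after a DLT | 1 DLT | 1 | Slows to one patient at a time; no pause |

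**Step 2: how much one death in six tells us.** The exact 95% (Clopper-Pearson) interval for 1/6 runs from the 2.5% point of Beta(1, 6) to the 97.5% point of Beta(2, 5), that is, 0.4% to 64.1%. The observation excludes neither a very low nor a very high fatality rate.

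**Step 3: how often the situation would arise.** Let q be the per-patient risk of a related death in the DLT window and d the risk of another DLT without death. Both are assumptions. A cohort advances with exactly one death when one patient dies and the other five have no DLT:

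P = 6 × q × (1 − q − d)^5

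| q | d = 0 | d = 10% |
|---|---|---|
| 2% | 6 × 0.02 × 0.98^5 = 10.8% | 6 × 0.02 × 0.88^5 = 6.3% |
| 5% | 6 × 0.05 × 0.95^5 = 23.2% | 6 × 0.05 × 0.85^5 = 13.3% |
| 10% | 6 × 0.10 × 0.90^5 = 35.4% | 6 × 0.10 × 0.80^5 = 19.7% |
| 15% | 6 × 0.15 × 0.85^5 = 39.9% | 6 × 0.15 × 0.75^5 = 21.4% |

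The 2% row is there because the nearest figure in the documents is 5/212 = 2.4%, over the whole of treatment with two of the three drugs.

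**Step 4: allow for the pooled two-death rule.** Take both arms at DL1 (12 patients) with no other DLTs. Two or more deaths, which would suspend enrollment, have probability 1 − (1 − q)^12 − 12q(1 − q)^11, or about 12%, 34% and 56% at q = 5%, 10% and 15%. Exactly one death, with both arms advancing, has probability 12q(1 − q)^11:
- 12 × 0.05 × 0.95^11 = 34%
- 12 × 0.10 × 0.90^11 = 38%
- 12 × 0.15 × 0.85^11 = 30%

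Pooling catches many two-death trials but leaves the one-death case open.

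**The case against.** The strongest reply is that a death would not pass unnoticed.
- An SAE goes to the sponsor's safety office within 24 hours (8.3). A death within 30 days that is not due to progression goes to the Clinical Director within one business day (7.3).
- The team meets about weekly. A grade 3 or 4 hemolytic anemia event requires a documented conference with the sponsor and both collaborators on the full safety profile (7.4.1), so fatal hemolysis that passes through those grades would be reviewed.
- The Safety Monitoring Committee meets about annually but may review more often if it sees the need (7.4.2).
- Accrual in the arm falls to one patient at a time.
- Section 3.1.2 makes expansion conditional on safety having been confirmed, and Section 13.1 allows suspension for unacceptable risk.
- Expansion patients receive two cycles without venetoclax and must meet Table 9 before it is added, with the 10.2 rules still active.

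All of this stands. A reader might infer from Table 8 that the plan has no death rule, or that a death needs no review. The documents support neither: 10.2 has a two-event rule that pools cohorts and counts grade 4 hemolytic anemia with deaths, and the duties above are required scrutiny. What they do not do is make a hold mandatory or tie a safety analysis to the dose decision. The reporting duties do not pause enrollment, the conference is triggered by one toxicity at grades 3 and 4, and the remaining provisions are discretionary. Section 3.1.2 gives no criterion of its own beyond Table 8.

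It is also fair to say that this is a design choice and not a contradiction between passages, and that the rates in the working are assumed.

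**Conclusion.** The point holds for exactly one probably or definitely related death among six patients in the DLT window with no other DLT. Table 8 then sends the dose to expansion, and no mandatory rule intervenes unless the death is an infection covered by the infection rule. Which histologies that rule covers is unclear: its context is MZL, but its count is of the first six subjects on the study.

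The size is 23%, 35% or 40% of six-patient cohorts at assumed death risks of 5%, 10% or 15% with no other DLTs, and 13% or 20% at 5% or 10% with a 10% rate of other DLTs. These describe what the rule would do at assumed rates; they are not forecasts for this regimen.

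A reader might prefer the overall probability that Table 8 advances the dose at those risks with no other DLTs: 97%, 89% and 78%. That overstates the defect, because it includes cohorts with no death at all (0.95^6 = 73.5%, 0.90^6 = 53.1%, 0.85^6 = 37.7%), in which a rule about deaths would change nothing. Only the one-death figures bear on the point.

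The gap is narrow but cheap to close, and it concerns the safety of patients receiving a new combination.

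**What to change.** Add a row to Table 8: any grade 5 event that meets the DLT relatedness definition holds enrollment in that arm until the safety analysis already prescribed in the DL(-1) row is done, before the dose is carried to expansion.

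In Section 10.2, cross-refer to the new row, reconcile it with the single-fatal-infection rule and the two-event rule, and state which histologies the infection rule covers.

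The outcome of the analysis, including any decision on dose, stays with the sponsor and investigators; the change fixes only when the analysis must happen.

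The cost is one table row, a cross-reference and a clarified sentence, plus a short enrollment pause in one arm after a related death. At the assumed risks with no other DLTs, the chance that a cohort passes straight to expansion would fall from 96.7% to 73.5% at 5% and from 88.6% to 53.1% at 10%. The difference is the one-death cohorts, which would be reviewed first and not necessarily stopped.

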### 3.1.2 Dose-Expansion Phase

Once safety is confirmed, expansion cohorts (Cohorts 3 and 4 and Arms 3 and 4) will be enrolled to collect additional safety information as well as disease response (Figure 5). During the dose expansion portion of the study, all patients will receive magrolimab with obinutuzumab for 2 cycles during the “window” period (i.e., Cycle -2 and Cycle -1) designed to assess for early clinical activity and correlates of response to magrolimab and obinutuzumab. The purpose of the window is to study the molecular and immunologic correlates of response to magrolimab-based therapy. It is not intended to provide complete information regarding the clinical activity of this doublet.

[figure not shown]
After completing the window, venetoclax will be added with the dose determined from the dose-finding cohorts as described above. Patients must fulfill the clinical and laboratory criteria mentioned in Table 9 below prior to addition of venetoclax. Patients with unequivocal PD during the treatment window who are tolerating therapy will be allowed to be moved immediately to the next phase (i.e., addition of venetoclax). After completion of Cycle 1, all patients will be treated with an additional five (5), 4-week cycles of triplet combination therapy (magrolimab and obinutuzumab and venetoclax). Final duration of therapy will be based on response to the first 6 cycles of triplet combination therapy. FL, MZL and MCL patients who achieve a CR and CLL patients who achieve a CR with undetectable peripheral blood MRD by flow cytometry after 6 cycles of triplet therapy will stop treatment but remain potentially eligible for an additional 6 cycles upon disease relapse provided that they still meet re-treatment criteria and the duration of CR is  $\geq$  6 months. Disease relapse is defined by conventional criteria for clinical relapse that is associated with radiographic progression. Additionally, for CLL patients, positive flow cytometry during follow-up will be considered relapsed for re-treatment. Reappearance of ctDNA is not considered disease relapse on this protocol. Patients who achieve a PR after 6 cycles of triplet combination therapy will be eligible to receive an additional 6 cycles and then will stop treatment.

**Table 9: Criteria for commencing treatment with triplet combination therapy**

[figure not shown]
| Parameter   | Value  |
|---|--|
| • ECOG PS   | 0-2  |
| • Absolute neutrophil count (ANC)                                     | $\geq 1,000 / \text{mm}^3$   |
| • Platelets   | $\geq 50,000 / \text{mcL}$ (transfusions permitted)  |
| • Hemoglobin  | $\geq 9.0 \text{ g/dL}$ (transfusions permitted)   |
| • Renal function  | Glomerular filtration rate (GFR) $\geq 30 \text{ mL/min/1.73 m}^2$ as estimated by the Modification of Diet in Renal Disease (MDRD) abbreviated formula. If not on target, a 24 hour urine creatinine clearance can be used to directly measure. |
| • Aspartate aminotransferase (AST) and alanine aminotransferase (ALT) | Patients without liver involvement with lymphoma $\leq 3.0 \times$ the upper limit of normal (ULN)
Patients with liver involvement with lymphoma $\leq 5.0 \times$ the upper limit of normal (ULN)  |

### 3.1.3 Study Schemas

[figure not shown]
**Figure 3: Arm 1: FL Dose-finding**

**Figure 4: Arm 2: MZL, MCL and CLL Dose-finding**

**Figure 5: Arms 3 and 4 – Dose Expansion**

### 3.1.4 Dose-Limiting Toxicity

Dose limiting toxicities (DLTs) will be assessed during the venetoclax dose-finding for Arms 1 and 2 as follows:

- the first 4 weeks of triplet combination therapy for patients enrolled in Arm 1, Cohort 1 (C1D1 to C1D28)

- the first 5 weeks after starting venetoclax in Arm 2, Cohort 2 (C1D1 to C1D35).

Dose reductions of magrolimab and obinutuzumab are not permitted during DLT assessment period.

A DLT for this study is defined as any grade 3 or higher adverse event that is clinically relevant and deemed probably or definitely related to any of the study drugs or to the combination therapy, in the opinion of the Principal Investigator and occurs during the venetoclax dose-finding period with the exception of following:

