#### 3.1.4.1 Non-hematologic AEs

- Grade 3 nausea, vomiting, or diarrhea that persist  $\leq$  7 days with supportive care
- Grade 3 fatigue with improvement to  $\leq$  grade 2 within 7 days
- Grade 3 infection that improves to  $\leq$  grade 2 after initiation of antimicrobials
- Grade 3 electrolyte disturbances that improve to  $\leq$  grade 2 within 72 hours with appropriate medical management and are not associated with other clinically significant consequences.
- Grade 3 magrolimab- or obinutuzumab-infusion reactions that resolve to  $\leq$  grade 1 within 24 hours. **NOTE:** In a patient, if it is not clear if the AE is an infusion-related reaction (IRR), the patient may be replaced.
- Other grade 3 laboratory abnormality that is asymptomatic and deemed by the investigator to be not clinically significant

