**Table 10: Intrapatient ramped-up dose-escalation schedule for venetoclax in MZL, MCL and CLL patients**

| Week of safety ramp-up period | Patients with MZL, MCL and CLL (Arms 2 and 4) |                |
|-------------------------------|---|----------------|
|                               | DL(-1):
200 mg                             | DL1:
400 mg |
| 1                             | 20 mg   | 20 mg          |
| 2                             | 50 mg   | 50 mg          |
| 3                             | 100 mg  | 100 mg         |
| 4                             | 200 mg  | 200 mg         |
| 5                             | 200 mg  | 400 mg         |

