**Table 11: Drug administration schedule for study medications for dose-finding cohorts**

| Arm | Drug a,b,c | Cycle 1
Arm 1: 28 days
Arm 2: 35 days  | Cycles 2-12
Arms 1 and 2: 28 days |
|-----|-----------------------|---|---|
| 1   | Magrolimab     | D2: 1mg/kg
D8,15,22: 30mg/kg   | D1,15: 30mg/kg                       |
|     | Obinutuzumab   | D1: 100mg
D2: 900mg
D8,15: 1000mg  | D1: 1000mg                           |
|     | Venetoclax     | D1-28:
DL1: 800mg
DL(-1): 600mg  | D1-28:
DL1 800mg
DL(-1) 600mg  |
| 2   | Magrolimab     | D2: 1mg/kg
D8,15,22: 30mg/kg   | D1,15: 30mg/kg                       |
|     | Obinutuzumab   | D1: 100mg
D2: 900mg
D8,15: 1000mg  | D1: 1000mg                           |
|     | Venetoclax     | DL1:
D1-7: 20mg
D8-14: 50mg
D15-21: 100mg
D22-28: 200mg
D29-35: 400mg

DL(-1):
D1-7: 20mg
D8-14: 50mg
D15-21: 100mg
D22-28: 200mg
D29-35: 200mg | D1-28:
DL1 400mg
DL (-1) 200mg |

a When both magrolimab and obinutuzumab are given on the same visit day, obinutuzumab will be administered at least 1 hour after the completion of magrolimab administration.

b Premedication with acetaminophen 650 mg and diphenhydramine 25-50mg (or comparable regimen) will be administered 30-60 minutes prior to all obinutuzumab doses. Similar premedication will also be given prior to priming dose and first loading dose of magrolimab. Additional premedication with dexamethasone 4 to 20 mg or comparable regimen will be given before the priming dose and first loading dose of magrolimab. Premedication is not required for subsequent doses of magrolimab.

c Obinutuzumab and magrolimab are administered as intravenous infusions.

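### In Arm 2, Table 8's move from DL1 to DL(-1) cannot reduce DLTs arising on days 1-28, and for some kinds of early DLT no safety review is required before DL(-1) opens

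*Combined protocol and SAP*

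**What the plan says.** Section 3.1.4 observes Arm 2 patients for DLTs over "the first 5 weeks after starting venetoclax in Arm 2, Cohort 2 (C1D1 to C1D35"). An event counts if it is probably or definitely related to any study drug or to the combination; the week of onset plays no part.

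The venetoclax steps are in Table 10 ("Intrapatient ramped-up dose-escalation schedule for venetoclax in MZL, MCL and CLL patients") and Table 11 ("Drug administration schedule for study medications for dose-finding cohorts"). Both levels take 20, 50, 100 and 200 mg in weeks 1 to 4. In week 5, DL1 goes to 400 mg and DL(-1) stays at 200 mg. Magrolimab and obinutuzumab are the same at both levels.

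Table 8 responds to two or more DLTs in six at DL1 with "Six (6) patients will be entered at dose level (-1"). Only if DL(-1) also has two or more in six does it say "Further enrollment will be stopped, and a safety analysis will be performed to determine further course of action".

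Section 3.1.1 slows entry: "If a DLT has occurred, only 1 patient can be in the respective DLT assessment period at a given time". Sections 3.1.4.1 and 3.1.4.2 exclude several early events, among them "Grade 3 magrolimab- or obinutuzumab-infusion reactions that resolve to" grade 1 or less within 24 hours, and "Grade 3 anemia that lasts less than 3 days and responds to blood transfusion".

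**The concern.** De-escalation helps when the lower level removes the exposure that caused the toxicity. In Arm 2 the lower level changes nothing before day 29. If two DL1 patients have DLTs on days 1-28, the cause lies in the shared ramp-up, the fixed-dose antibodies or their combination, and DL(-1) gives up to six more patients the same four weeks.

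Early events are plausible. Section 1.2.8.1 says magrolimab and obinutuzumab had not been studied together, and dose-finding patients start both in Cycle 1. Section 1.2.5.1 places TLS after the first venetoclax dose or a ramp-up step. In the venetoclax-obinutuzumab CLL study in section 1.2.7.1, all three TLS cases came before venetoclax. After the exclusions, grade 4 or persistent grade 3 infusion reactions, hemolytic anemia requiring hospitalization, and clinical TLS of grade 3 or higher can still count.

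Two things are at stake: repeat exposure of a few patients, and a dose choice. If DL(-1) passes by chance, 200 mg goes forward to up to 6 + 12 + 6 = 24 MZL, MCL and CLL expansion patients for a reason unrelated to the 400 mg dose, and Table 8's safety analysis is never reached.

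**Working it through.** **The plan's own figure.** Two arms × two levels × 6 = 24 dose-finding patients, as section 10.2 states. With 18 + 6 + 12 + 6 = 42 in expansion, the total is 66, also as stated.

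**Schedules side by side (Tables 10 and 11).** Cumulative venetoclax to day 28 is 7 × (20 + 50 + 100 + 200) = 2,590 mg at both levels. To day 35 it is 2,590 + 7 × 400 = 5,390 mg at DL1 and 2,590 + 7 × 200 = 3,990 mg at DL(-1). The only days that differ are 29 to 35.

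**Chance of the path.** Let s be the day 1-28 DLT risk per patient. The documents give none for this triplet, so 5%, 10% and 20% are assumed. Assume also no week-5 DLTs, and the same s at both levels.

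- DL1 fails: F = 1 − (1 − s)^6 − 6s(1 − s)^5
- DL(-1) then passes: 1 − F
- Both happen: F × (1 − F)
- Patients entered at DL(-1), one at a time, stopping at the second DLT or at six: E = sum over k = 0 to 5 of P(Bin(k, s) ≤ 1)
- Expected extra patients, not conditional on DL(-1) opening: F × E

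| s | F | 1 − F | F × (1 − F) | E | F × E |
|---|---|---|---|---|---|
| 5% | 0.0328 | 0.967 | 0.032 | 5.95 | 0.2 |
| 10% | 0.1143 | 0.886 | 0.101 | 5.83 | 0.7 |
| 20% | 0.3446 | 0.655 | 0.226 | 5.41 | 1.9 |

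Section 3.1.1 allows two patients in the window until a DLT occurs, so E could be slightly higher, but never above 6.

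**When de-escalation works.** If all DLTs come from 400 mg in week 5 (assumed 30% at DL1, 0 at DL(-1)), the chance of two or more in six falls from 0.580 to 0. With 10% early risk at both levels and 20% week-5 risk at DL1 only, it falls from 0.536 to 0.114. With 30% early risk alone it stays at 0.580.

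**Where s may lie.** Section 1.2.7.2 cites three regimens containing venetoclax and obinutuzumab: no DLT at any level in the MCL study (no DLT denominator given), 1 in 22 (4.5%) and 1 in 31 (3.2%). At the last two rates, F is 0.027 and 0.014. None of the three included magrolimab.

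**Which early DLT pairs already require review.**

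| Pattern | Rule |
|---|---|
| Any grade 3-4 hemolytic anemia | Section 7.4.1: confer with the sponsor and both companies |
| Two related deaths or grade 4 hemolytic anemias | Section 10.2: suspend enrollment, formal assessment |
| Infection events in MZL | Section 10.2: hold, safety analysis |
| Two nonfatal DLTs of another kind (TLS, grade 4 or persistent infusion reaction) | None before DL(-1) |

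Section 10.2's rule on 25% of patients unable to complete therapy starts only after 20 patients are enrolled.

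**The case against.** A reader might infer that DL(-1) opens with no safety review of any kind. The documents do not support that. The research team meets about weekly to discuss each patient (section 7.4.1), de-escalation is described there as a decision of which both companies are told, and the rules tabulated above cover hemolytic anemia, deaths and MZL infections. What remains is narrower: Table 8 requires no analysis, and no other rule requires one for the last pattern in that table.

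A reader might also infer that DL(-1) is pointless. It is not. It halves venetoclax on days 29-35 and in Cycles 2-12, and the target dose is what is being tested. Shared early steps follow from a stepped ramp-up adopted to limit TLS, and section 3.1.5 already lets an individual with a ramp-up DLT drop to a tolerated dose. All of this stands; none of it changes the day 1-28 risk for the next six patients.

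The pass probabilities of 97%, 89% and 66% look alarming only if one forgets that DL(-1) must first open. At 5% to 10% true risk, two DLTs in six would be largely chance, and a pass at DL(-1) would not be a safety failure. The cited DLT experience does not reach 20%. The exclusions, the relatedness requirement and the option to replace a patient whose infusion reaction is unclear all push the countable rate down. This objection stands and limits the size of the point.

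Expansion patients receive both antibodies for two cycles before venetoclax (Table 12), so they do not repeat the same combined first four weeks. For them the consequence is one of dose choice.

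**Conclusion.** The point holds in a limited form. In Arm 2, moving to DL(-1) cannot reduce DLTs that arise on days 1-28, and two such DLTs outside the categories already covered lead to up to six more patients without a mandated review. The unconditional chance of the full path is about 3%, 10% and 23% at assumed early risks of 5%, 10% and 20%, with about 0.2, 0.7 and 1.9 extra patients expected. These figures rest on an assumed risk, equal at both levels, and on no week-5 DLTs; cited experience suggests the low end or below, without magrolimab. Arm 1 is unaffected, because 800 and 600 mg differ from day 1. This is a cheap improvement to consider, not a defect that undermines dose-finding.

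**What to change.** Add an Arm 2 row to Table 8: *Two or more of 6 patients at DL1 with DLT onset on C1D1 to C1D28, or before the first 400 mg dose if ramp-up was interrupted: Arm 2 enrollment stops and a safety analysis is done before DL(-1) may open.* All other patterns of two or more in six go to DL(-1) as now. That includes one early plus one late DLT, which the row leaves alone because one event may relate to 400 mg.

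Section 8.2 already collects the onset date of every adverse event, and Table 11 then gives the scheduled dose. The actual venetoclax dose at DLT onset needs noting, mainly for interrupted ramp-ups. The 35-day window, 2-of-6 threshold, exclusions, stagger and maximum of 24 patients do not change.

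The cost is one table row and a possible pause in Arm 2 for an analysis the plan already prescribes one step later. DL(-1) can still open afterward if judged useful.
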